## Is a congenital anomaly/birth defect

#### Other situations:

- Medical or scientific judgment will be exercised by the investigator in deciding whether SAE reporting is appropriate in other situations such as significant medical events that could jeopardize the participant or require medical or surgical intervention to prevent one of the other outcomes listed in the above definition. These events are usually considered serious.
- Examples of such events include invasive or malignant cancers, intensive treatment for allergic bronchospasm, blood dyscrasias, convulsions or development of intervention dependency or intervention abuse.
- Suspected transmission of any infectious agent via the IMP will also be considered an SAE.

## 10.3.3. Recording and Follow-Up of AE and/or SAE

## AE and SAE Recording

- When an AE/SAE occurs, it is the responsibility of the investigator to review all
  documentation (eg, hospital progress notes, laboratory reports, and diagnostics reports)
  related to the event.
- The investigator will then record all relevant AE/SAE information.
- It is **not** acceptable for the investigator to send photocopies of the participant's medical records in lieu of completion of the required form.
- There can be instances when copies of medical records for certain cases are requested. In this case, all participant identifiers, with the exception of the participant number, will be redacted on the copies of the medical records before submission.
- The investigator will attempt to establish a diagnosis of the event based on signs, symptoms, and/or other clinical information. Whenever possible, the diagnosis (not the individual signs/symptoms) will be documented as the AE/SAE.

## **Assessment of Severity**

The investigator will assess intensity for each AE and SAE reported during the study.

All AEs observed will be graded using the NCI CTCAE (version 5.0) definitions.

The grade refers to the severity of the AE. If a particular AE's severity is not specifically graded by the guidance document, the investigator is to use the general NCI CTCAE definitions of grade 1 through grade 5 following his or her best medical judgment, using the following general guideline:

- Grade 1: Mild; asymptomatic or mild symptoms; clinical or diagnostic observations only; intervention not indicated
- Grade 2: Moderate; minimal, local or noninvasive intervention indicated; limiting ageappropriate instrumental ADL (eg, preparing meals, shopping for groceries or clothes, using the telephone)
- Grade 3: Severe or medically significant but not immediately life-threatening; hospitalization or prolongation of hospitalization indicated; disabling; limiting self-care ADL (ie, bathing, dressing and undressing, feeding self, using the toilet, taking medications, and not bedridden)
- Grade 4: Life-threatening consequences or urgent intervention indicated
- Grade 5: Death related to AE

NOTE: An AE that is assessed as severe may not necessarily meet the criteria for an SAE. Severe is a category used for rating the intensity of an event; and both AEs and SAEs can be assessed as severe. An event is defined as "serious" when it meets at least 1 of the predefined outcomes as described in the definition of an SAE, not when it is rated as severe. Grade 4 and 5 AEs are always assessed as serious (ie, SAE).

#### Assessment of Causality

• The investigator is obligated to assess the relationship between IMP and each occurrence of each AE/SAE as **related** or **not related**. The investigator will use clinical judgment to determine whether there is reasonable possibility that the IMP caused the AE.

- A reasonable possibility of a relationship conveys that there are facts, evidence, and/or arguments to suggest a causal relationship, rather than a relationship cannot be ruled out.
- Alternative causes, such as underlying disease(s), concomitant therapy, and other risk
  factors, as well as the temporal relationship of the event to IMP administration, will be
  considered and investigated.
- Related means that the AE cannot be explained by the participant's medical condition, other
  therapies, or an accident. The temporal relationship between the AE and IMP administration
  is compelling and/or follows a known or suspected response pattern concerning that IMP.
- Not related means that the AE can be readily explained by other factors such as the
  participant's underlying medical condition, concomitant therapy, or accident. No plausible
  temporal or biologic relationship exists between the IMP and the AE.
- The investigator will also consult the investigator's brochure (IB) and/or product information, for marketed products, in his/her assessment.
- For each AE/SAE, the investigator must document in the medical notes that they have reviewed the AE/SAE and has provided an assessment of causality.
- There could be situations in which an SAE has occurred, and the investigator has minimal
  information to include in the initial report. However, it is very important that the
  investigator always assess causality for every event before the initial transmission of the
  SAE data.
- The investigator could change his/her opinion of causality in light of follow-up information and send an SAE follow-up report with the updated causality assessment.
- The causality assessment is one of the criteria used when determining regulatory reporting requirements.

### Follow-up of AEs and SAEs

- The investigator is obligated to perform or arrange for the conduct of supplemental
  measurements and/or evaluations as medically indicated or as requested to elucidate the
  nature and/or causality of the AE or SAE as fully as possible. This could include additional
  laboratory tests or investigations, histopathological examinations, or consultation with other
  health care professionals.
- If a participant dies during participation in the study or during a recognized follow-up period, the investigator will provide a copy of any postmortem findings including histopathology.
- The investigator will submit updated SAE data within 24 hours of receipt of the information.

### 10.3.4. Reporting of SAEs and AESIs

## SAE and AESI reporting

- All SAEs and AESIs will be recorded on the AE form of the eCRF. SAEs will also be recorded on the paper SAE report form.
- The investigator or designated site staff will ensure all entered data are consistent.

- An alert email for the SAE and AESI reports on the eCRF will automatically be sent by email to the sponsor or designee's safety mailbox via the EDC system.
- The paper SAE report form will be faxed or emailed to the sponsor's designee (see the Serious Adverse Event Reporting details on page 2 of this protocol).

# **10.4.** Appendix 4: Contraceptive and Barrier Guidance

## 10.4.1. Women of Childbearing Potential Definition

A female is considered a WOCBP unless she is either:

- a. Postmenopausal: A postmenopausal state is defined by continuous amenorrhea for at least 1 year without an alternative medical cause with an FSH measurement of >40 IU/L. If a postmenopausal woman is using hormonal therapy, such as hormone replacement therapy or hormonal contraceptives, FSH levels might be suppressed and therefore an FSH test to confirm a postmenopausal state is not considered valid. In this case the postmenopausal state will need to be assessed by the investigator.
- b. Surgically sterilized: Women who have had a documented permanent sterilization procedure (eg, hysterectomy, bilateral salpingectomy, or bilateral oophorectomy)

# 10.4.2. Contraception Guidance

## 10.4.2.1. Female Contraception for Women of Childbearing Potential

WOCBP must use one of the following contraception methods from signing the ICF until the last dose of IMP:

The following Clinical Trials Facilitation and Coordination Group acceptable methods are permitted for efgartigimod studies:

- Progestogen-only oral hormonal contraception in which inhibition of ovulation is not the primary mode of action
- Male or female condom with or without spermicide
- Cap, diaphragm, or sponge with spermicide

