; AE=adverse event; BL=baseline; COMPASS=composite autonomic symptom scale; Conmed=concomitant medications; CRP=C-reactive protein; ESR=erythrocyte sedimentation rate; IMP=investigational medicinal product; MaPS=Malmö POTS Symptom Score; PD=pharmacodynamics; PGI-C=Patient Global Impression – Change; PGI-S=Patient Global Impression – Severity; PK=pharmacokinetics; POTS=postural orthostatic tachycardia syndrome; PROMIS=Patient-Reported Outcomes Measurement Information System; QW = once weekly; Q2W = every 2 weeks; TSH=thyroid stimulating hormone; W=week; WOCBP=women of childbearing potential.

<sup>a With the exception of informed consent, eligibility check, and IMP infusion, assessments at BL are conducted as part of the ARGX-113-2104 study.

- b Questionnaires will be administered in the following order: MaPS, PGI-S past week recall, PROMIS Fatigue, PROMIS Cognitive Function, COMPASS 31, PGI-S 2-week recall, PGI-C.
- c Procedure performed as part of the ARGX-113-2104 study week 24 assessments
- d These assessments may be performed over 1 to 2 days at each time point, as long as all testing is completed prior to dosing scheduled for that time point.
- e The physical examination will comprise a full assessment of systems at baseline and a brief assessment at all other time points.
- f The 10 mg/kg efgartigimod dose is based on body weight, and the maximum total dose per efgartigimod infusion is 1200 mg for participants who weigh ≥120 kg. The dose level will be recalculated if a participant's weight has changed (increased or decreased) by more than 10% from baseline.
- g Vital signs will be measured before collecting any blood sample or administering IMP infusions.
- h A urine pregnancy test will be conducted for WOCBP at baseline and during the study, including during the follow-up period. On visits where both pregnancy testing and IMP administration will be performed, all pregnancy testing must be performed predose. Dosing should not begin until a negative pregnancy test result has been confirmed.
- i Blood samples to be collected predose (except for week 48, where no IMP is administered and the sample can be taken at any time during the visit).

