#### 4. STUDY DESIGN

# 4.1. Overall Design

Study ARGX-113-2105 is a long-term, single-arm, open-label, multicenter extension of the ARGX-113-2104 study, designed to evaluate the long-term safety of efgartigimod IV in adult patients with PC-POTS. Participants will be enrolled from both active and placebo arms of the ARGX-113-2104 study and will receive efgartigimod IV 10 mg/kg in the extension study without knowledge of their prior treatment arm. To be eligible to enroll in this study, participants must have completed the 24-week treatment period of the ARGX-113-2104 study and must not have permanently discontinued the IMP in that study.

The treatment period of this study is 48 weeks. Participants will receive efgartigimod (10 mg/kg) by IV infusion QW for the first 4 weeks (induction dosing period), and then Q2W for 42 weeks (maintenance dosing period). Efgartigimod will be administered during the treatment period in an approximately 1-hour IV infusion by site staff or a home nurse. If clinically indicated (eg, the participant loses PC-POTS symptom control), the participant and investigator, based on the participant-reported reason for the request and physical examination, can jointly decide to return the participant to QW dosing during the maintenance dosing period. Participants who switch back to QW dosing will not be allowed to switch back to Q2W dosing during the study. Participants who switch must attend an unscheduled visit (see Table 2). The decision to switch to QW dosing and the date of the switch should be recorded in the eCRF. The final dose for participants who remain on Q2W dosing will be administered at week 46 (day 323). The final dose for participants who switch back to QW dosing during the maintenance dosing period will be administered at week 47 (day 330). The end of treatment visit occurs on week 48 (day 337).

Participants will return for a safety follow-up visit approximately 56 days after the last dose of IMP administration. The total planned duration of the study is 386 days.

IMP infusions must occur at the site for a minimum of 3 consecutive visits (baseline visit and the week 1 and 2 visits) before home infusions are allowed. If doses are missed at 1 or more of these visits, then dosing at subsequent visits will also be on-site. IMP administration at home will not commence until after 3 doses have been administered on-site.

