### 4.4. End-of-Study Definition

The end-of-study is defined as the date of the last participant's last visit.

A participant will have completed the study if the SFV has been completed.

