## 5.2. Exclusion Criteria

Participants will be excluded from the study if any of the following criteria apply:

- 1. The participant has a clinically significant condition, based on the judgement of the Study Investigator, eg, laboratory abnormalities, 12-lead ECG readings, concomitant medical disease(s), etc., which may place them at undue risk or confound interpretation of study data.
- 2. The participant intends to become pregnant or start breastfeeding during the study.

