## 6.9.1. Prohibited Medication

The following medications or treatments are not permitted while the participant receives IMP:

- Subcutaneous or IV Ig
- Plasma exchange/plasma electrophoresis
- Live or live-attenuated vaccines (this restriction also applies for up to 28 days after the final dose of IMP)
- IV saline bolus treatments for volume expansion for treating POTS symptoms

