# 8.3.5. Pregnancy Testing

- WOCBP will be tested for pregnancy. Urine tests for pregnancy will occur at the time
  points specified in the SoAs (Section 1.3). On visits where both pregnancy testing and
  IMP administration will be performed, all pregnancy testing must be performed
  predose. Dosing should not begin until a negative pregnancy test result has been
  confirmed.
- Pregnancy testing in WOCBP will be conducted at the end of relevant systemic exposure (ie, at the SFV).

- Additional pregnancy testing could be performed, as necessary by the investigator or required by local regulations, to establish the absence of pregnancy at any time during the study.
- Any pregnancy reported during a clinical research study, including the safety follow-up period, is routinely monitored as standard practice. The pregnancy could have arisen from a female clinical study participant or a male participant's female partner. In either situation, consent will be requested to collect medical information about the pregnancy and the baby's health for up to 12 months after the baby's birth.

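### Required contraception ends at the last dose, but the protocol places the end of relevant systemic exposure at the safety follow-up visit about 56 days later, and does not explain the difference

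*Protocol*

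**What the plan says.** Protocol Section 10.4.2.1 sets the contraception period: "WOCBP must use one of the following contraception methods from signing the ICF until the last dose of IMP". Inclusion criterion 3 (Section 5.1) asks for contraceptive use in line with local regulations and points to Section 10.4.2 for the requirements. It adds no later end date.

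Section 8.3.5 sets the last pregnancy test and, in doing so, says when relevant exposure ends: "Pregnancy testing in WOCBP will be conducted at the end of relevant systemic exposure (ie, at the SFV").

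Section 4.1 gives the timing of that visit: "Participants will return for a safety follow-up visit approximately 56 days after the last dose of IMP administration". Table 2 (footnote d) and Section 7.1.1 make it 56 ± 3 days after the final dose, and Section 7.1.1 applies this to early discontinuers as well.

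Other provisions also run to the SFV. Section 4.4 states that "A participant will have completed the study if the SFV has been completed". The footnote on pregnancy tests in the Schedule of Activities says that "A urine pregnancy test will be conducted for WOCBP at baseline and during the study, including during the follow-up period". Sections 8.3.5 and 8.4.5 provide for reporting and following up pregnancies, including those that arise in the safety follow-up period.

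**The concern.** The protocol has one measure that prevents pregnancy during exposure, the contraception requirement. It ends on the day of the last dose. The protocol then describes the following eight weeks or so as still within relevant systemic exposure, and it keeps testing for pregnancy and recording it over that time. A reader cannot tell whether the earlier contraception end date is deliberate or whether one of the two sections was written without the other in view.

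What is at stake is participant safety and the accuracy of what participants are told. A site that follows Section 10.4.2.1 as written may tell a woman that the study no longer requires contraception after her last infusion, while Section 8.3.5 treats her as still exposed. Once dosing has ended, the remaining pregnancy rule in Section 7.1.1, permanent discontinuation of study drug, has nothing to act on.

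**Working it through.** This is day arithmetic on the protocol's own schedule.

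**Inputs**
- Last dose on Q2W: Section 4.1, "The final dose for participants who remain on Q2W dosing will be administered at week 46 (day 323").
- Last dose on QW: week 47, day 330 (Section 4.1).
- Interval from last dose to SFV: 56 days, window ± 3 days (Section 4.1; Table 2, footnote d; Section 7.1.1).
- End-of-treatment visit: week 48, day 337, with a pregnancy test (Table 1).
- Planned study duration: 386 days (Section 4.1).

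**Step 1. Check the calendar against the protocol's own figures.** Study day = 7 × week + 1.
- Week 46: 7 × 46 + 1 = 323.
- Week 47: 7 × 47 + 1 = 330.
- Week 48: 7 × 48 + 1 = 337.
- Latest planned SFV: 330 + 56 = 386, which matches the stated duration.

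So the protocol counts the 56 days from the last dose, as assumed here.

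**Step 2. Interval between the end of required contraception and the stated end of relevant exposure.** Interval = SFV day − last dose day.

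| Participant | Contraception requirement ends | SFV (range with ± 3 days) | Interval | Share of days to SFV |
|---|---|---|---|---|
| Stays on Q2W | day 323 | 323 + 56 = 379 (376 to 382) | 56 days (53 to 59) | 56/379 = 14.8% |
| Returns to QW | day 330 | 330 + 56 = 386 (383 to 389) | 56 days (53 to 59) | 56/386 = 14.5% |
| Early discontinuation | day of last dose | last dose + 56 (± 3) | 56 days (53 to 59) | depends on date |

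**Step 3. Scheduled pregnancy tests in that interval.**
- Completers are tested at week 48, which is 337 − 323 = 14 days after the last Q2W dose or 337 − 330 = 7 days after the last QW dose.
- The next scheduled test is at the SFV, 379 − 337 = 42 days later (Q2W) or 386 − 337 = 49 days later (QW).
- Early discontinuers have a test at the IMP discontinuation or early discontinuation visit, and one at the SFV (Table 2).
- Section 8.3.5 also allows extra tests at any time, when the investigator finds them necessary or local rules require them.

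All of these tests find a pregnancy after it has begun.

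**Step 4. Look for an explanation.** Sections 5.1, 8.3.5, 8.4.5 and 10.4 give no reason for ending contraception in WOCBP before the SFV. The amendment summary places the drug in a low reproductive-risk category, but it uses this to remove the male contraception requirement, not to set the end date for women.

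**The case against.** The strongest reply is that nothing here conflicts in operation. Section 10.4.2.1 sets a contraception period and Section 8.3.5 times a test; a participant can satisfy both. The mention of the SFV as the end of exposure sits in a parenthesis within a bullet about testing, and may not have been meant as a definition. This stands as far as it goes: the end points are misaligned, and it would be wrong to say that the provisions contradict each other. But the parenthesis does equate the end of relevant exposure with the SFV, and no other section corrects that.

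The earlier end date may also be deliberate. Amendment 1 aimed to align contraception with the parent study and cites the low risk category. The Investigator's Brochure and the contraception guidance that the protocol cites might support it, and local regulations could require longer use at some sites. Table 2 also omits the PK sample at an IMP discontinuation visit held more than 4 weeks after the last dose, but gives no reason that bears on this question. All of this is possible, and it is why a stated rationale would be an acceptable answer. None of it appears in the protocol as the reason for the end date in WOCBP.

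Three stronger readings may tempt a reader, and the documents do not support them.
- **That a woman who decides to conceive after her last dose breaches Section 5.2.** The criterion, "The participant intends to become pregnant or start breastfeeding during the study", is an entry criterion about intent, and Section 5.4 applies the criteria before study drug is given. A later decision does not breach it. A woman who already intends at entry to conceive before the SFV would be excluded, which narrows the gap.
- **That the live-vaccine rule in Section 6.9.1 shows yet another exposure period.** That rule says "this restriction also applies for up to 28 days after the final dose of IMP", but the protocol ties it neither to pregnancy nor to an exposure period. It need not match the contraception end date.
- **That a pregnancy in the interval could be found at two scheduled tests and in no other way.** Discretionary tests are allowed, and reported pregnancies are sent to the sponsor within 24 hours and followed up, with information on the infant for up to 12 months after birth if consent is given.

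**Conclusion.** The point holds as a misalignment between Sections 10.4.2.1 and 8.3.5. Required contraception in WOCBP ends 53 to 59 days before the protocol's stated end of relevant systemic exposure, and the protocol does not say why. The interval applies to every dosed WOCBP, on either dosing schedule and after early discontinuation.

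This rests on reading the parenthesis in Section 8.3.5 as the protocol's statement of when relevant exposure ends, and on the SFV taking place in its window. The 53 to 59 days measure how far apart the two end points are; they are not a measure of risk. The number of WOCBP among the roughly 38 expected participants is not stated. The consent form is not among the documents reviewed, so no gap in it is claimed. Which end point is right cannot be judged from these documents. No endpoint, analysis or statistical figure is affected.

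**What to change.** The sponsor should reconcile Sections 10.4.2.1 and 8.3.5 from its own exposure and reproductive-risk data. Any one of three routes would resolve the point:
- align the contraception end date with the stated end of relevant exposure;
- reword the statement in Section 8.3.5 about when relevant exposure ends;
- keep both and add a sentence giving the reason for the difference.

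The choice is the sponsor's. Whichever is made, the participant information should say the same thing.

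The cost is protocol wording and a check of the participant information. No visit or test is added, since the SFV and its pregnancy test are already scheduled. Sections 5.2 and 6.9.1 need no change for this purpose.

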## 10.4.2.2. Male Contraception

No male contraception is required.

# 10.5. Appendix 5: Operational Considerations for COVID-19 Risk Mitigation

Participants will be tested for SARS-CoV-2 if they are symptomatic or if applicable law requires testing; if applicable, a negative polymerase chain reaction test (central or local laboratory) is required within 72 hours before enrollment regardless of a participant's vaccination status.

During the study, the sites will implement all recommendations issued by the local government regarding the spread of COVID-19, including specific guidelines related to clinical research performed in clinical research centers.

This appendix is intended for use only if unforeseen changes in the COVID-19 pandemic result in new restrictions at the site or new risks for participants or site staff from attending visits at the site.

Additional testing for COVID-19 beyond what is listed in the SoAs (Section 1.3) is not required during the study unless required by local authorities. However, it is recommended that participants who develop COVID-19 symptoms while receiving IMP be tested, with results reported for the study.

